4.6 General Concomitant Medication and Supportive Care Guidelines

Patients may receive other medications that the investigator deems to be medically necessary, with the specific exception of non-protocol specified chemotherapy, radiotherapy, anti-neoplastic biological therapy or other investigational agents. Patients who require the use of any of the aforementioned treatments for clinical management should be removed from the study.

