4.6.2 Anticonvulsants

No data exist regarding the interaction of pamiparib (BGB-290) with enzyme-inducing anti-epileptic drugs (EIAEDs). For this study, patients may **not** be on EIAEDs; patients who require anti-epileptic drugs (AED) may be on non-enzyme inducing anti-epileptic drugs (NEIAED). If a patient on this study protocol needs to have an AED started or needs to have a second AED added then only NEIAED should be used. There must be a ≥ 10 day period from discontinuation of an EIAED and initiation of therapy. In the event that an EIAED drug must be used for a patient on study the patient will be removed from the protocol.

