5.2.1 Dose Modification for Temozolomide and Pamiparib (BGB-290)

Dose reductions are required as indicated in the toxicity table above for any dose limiting toxicity (as defined in Section 5.1). Dosing will stop until the DLT has resolved to \leq grade 1 [or tolerable grade 2 for non-hematologic toxicity] or \leq baseline. The maximum length of time that pamiparib (BGB-290) and TMZ can be held is 21 days, or as stipulated in the table. After resolution, the dose of TMZ will be modified as stipulated below, with a maximum of 2 dose reductions. If treatment-related toxicity is not resolved in \leq 21 days (or as stipulated), the patient will be considered for monotherapy with pamiparib (BGB-290). If there is any question, the ABTC Central Office and the study chair should be contacted.

Dose level	Temozolomide dose	Dose reduction 1	Dose reduction 2
1 (starting dose)	20 mg QD Days 1-28	20 mg QD Days 1-21	20 mg QD Days 1- 14
-1	20 mg QD Days 1-21	20 mg QD Days 1-14	20 mg QD Days 1-7
-2	20 mg QD Days 1-14	20 mg QD Days 1-7	Either off study or pamiparib (BGB- 290) alone
-3	20 mg QD Days 1-7	Either off study or pamiparib (BGB-290) alone	N/A

TMZ Dose Reduction Schedule

ABTC # 1801

Blood counts will be evaluated weekly. Within -5 days prior to first dose of each cycle the patient must have an ANC \geq 1500/ul and platelet count \geq 100,000/ul. On Day 1 of each cycle (within -5 days) all **non-hematological** toxicity grade 3 or 4 (except for alopecia, nausea and vomiting) must have resolved (CTCAE grade \leq 1). If toxicity persists, treatment should be delayed by one week for up to 3 consecutive weeks. If after 3 weeks of delay all toxicity has still not resolved then any further treatment with temozolomide should be stopped (patient is off treatment).

If pamiparib (BGB-290) must be modified as stipulated in the Toxicity Management Table, the dose of pamiparib (BGB-290) will be modified as shown below, with a maximum of 2 dose reductions.

PI: [name]

NCI # ABTC-1801

PI: [name]

Dose Level	Pamiparib (BGB-290)					
Starting dose	60 mg b.i.d.					
First dose reduction	40 mg b.i.d.					
Second dose reduction	20 mg b.i.d.					

Pamiparib (BGB-290) Dose Reduction Schedule

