8.3 Safety Assessments

Safety assessments will consist of monitoring and recording all adverse events and serious adverse events, the regular monitoring of hematology and blood chemistry, pregnancy testing (in women of childbearing potential), regular measurement of vital signs, and the performance of physical/neurological examinations; ECGs and other cardiac monitoring may be performed as necessary.

Monitoring Pregnancy

Pregnancy in itself is not regarded as an AE or SAE, however all reports of congenital abnormalities/birth defects, elective terminations for medical reasons and any serious complications of pregnancy (including spontaneous miscarriage, still birth and blighted ovum) should be reported as SAEs.

In the event of any occurrence of pregnancy in a patient or the female partner of a male patient, the site will complete and submit (via email of fax) the Pregnancy Notification Report (Appendix 5) within 24 hours of awareness. All pregnancy follow-up information should be sent to COV PV using the Pregnancy Follow-up Report (Appendix 6). Pregnancy Appendix 5 and 6 can be found at the ABTC Consortium Website www.abtconsortium.org

Monitoring of the patient should continue until conclusion of the pregnancy. The outcome of all pregnancies (live birth, spontaneous miscarriage, elective termination, or congenital abnormality/birth defects) must be followed up and documented, including patients who have discontinued the study, provided that the patient/partner provides consent. In addition, information about the pregnancy, the birth of the baby, and the health of the baby for up to 8 weeks after birth, even after study treatment has stopped, should be collected.

A female study participant who becomes pregnant must be withdrawn from the study; however, male study participants whose partner becomes pregnant can remain in the study.

Pregnancy cases will be followed-up every 3 months until final pregnancy outcome has been provided and a request for the outcome will also be issued within two weeks of the anticipated delivery date. Pregnancy reports will be tracked on a separate tab of the SAE tracker.

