10.1 Off-Treatment Criteria

- 1. Disease Progression: Remove patient from protocol therapy at the time progressive disease is documented. Disease progression is defined as: Progressive neurologic abnormalities not explained by causes unrelated to tumor progression (e.g. anticonvulsant or corticosteroid toxicity, electrolyte abnormalities, hyperglycemia, etc.) or a greater than 25% increase in the measurement of the tumor by MRI scan. If neurologic status deteriorates, on a stable or increasing dose of steroids, or if new lesions appear on serial MRI, further study treatment will be discontinued. Please refer to the Imaging Core Manual for further imaging requirements and submission information.
- 2. Adverse Event:
 - Intercurrent illness that prevents further administration of treatment
 - Patients who experience unacceptable toxicity. Patients removed from study for unacceptable adverse events will be followed until resolution or stabilization of the adverse event.
- 3. Patient Withdrawal: Patient's refusal to continue treatment: in this event, document the reason for withdrawal.
- 4. Non-Compliance: Failure to comply with protocol (as judged by the investigator such as compliance below 80%, failure to maintain appointments, etc.)
- 5. Physician Decision: If at any time the treating physician feels the constraints of this protocol are detrimental to the patient's health remove the patient from protocol therapy.

ABTC # 1801

PI: [name]

- 6. Protocol Defined Delay:
 - Patients will be off treatment who experience a treatment-related toxicity causing a delay in treatment >21 days. Note: Patients who experience grade 3 hepatic toxicity will be off treatment if treatment-is delayed >14 days.
 - Delay in protocol >28 days for major events or other non-treatment related delays
 - Patients who require >2 dose reductions
- 7. Death

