10.2 Off-Study Criteria and Survival Follow-Up

Patients will only be off study at the time of death. Patients will be followed every two months for progression, for up to one year from the off-treatment date. All patients will be followed for survival every 2 months for the first 2 years from the off-treatment date; after 2 years, patients will be followed every 6 months until death. Survival status may be obtained by phone call, clinic visit, or medical records (e.g. physician notes/laboratory results of clinic or hospital visit).

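### Sections 4.6 and 8.3, and two rows of the 5.2.1 table, take living patients off the study, while 10.2 allows this only at death; PFS follow-up is the main exposure.

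*Combined protocol and SAP*

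**What the plan says.** Section 10 separates two states. Section 10.1 lists reasons for stopping treatment. Section 10.2 governs leaving the study and is categorical: "Patients will only be off study at the time of death". It asks for progression follow-up every two months for up to one year from the off-treatment date. Survival follow-up is every two months for two years and then every six months until death. Sections 4.1, 4.2 and 4.3 each repeat that all patients are followed for survival.

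Other sections use different language for living patients:

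- Section 4.6, where a patient needs an investigational agent, radiation, or a cytotoxic or biological anticancer drug from outside the protocol: "Patients who require the use of any of the aforementioned treatments for clinical management should be removed from the study".
- Section 8.3, on pregnancy: "A female study participant who becomes pregnant must be withdrawn from the study".
- Section 5.2.1, TMZ Dose Reduction Schedule: "Either off study or pamiparib" alone. This is the second-reduction entry for starting level -2 and the first-reduction entry for starting level -3.
- Section 4.6.2, on enzyme-inducing anti-epileptic drugs: "In the event that an EIAED drug must be used for a patient on study the patient will be removed from the protocol". This is ambiguous, because it could mean the study or only protocol therapy.

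Section 11 defines PFS and OS with censoring only by reference to the data cut-off. It has no rule for a patient removed from the study or for one who starts new anticancer therapy before progression.

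**The concern.** The instructions cannot all be followed literally. A site that acts on 10.2 keeps following a patient who has started salvage therapy. A site that acts on 4.6 may record the patient as off study and stop. The second patient would then be censored in practice at the last assessment, although Section 11 plans no such censoring.

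This matters most for new anticancer therapy. A patient who is given it before progression has been called is plausibly closer to progression than the patients who remain. Kaplan-Meier estimation assumes that censored patients have the same future risk as those still followed. If their risk is higher, the PFS curve is too favorable. OS is affected in the same way if survival contact also ends. Each Phase II cohort has a single arm, so no control group shares the bias, and its extent would depend on which section each site follows.

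**Working it through.** **Comparing the passages.** The plan states no figure on this point, so the main check is textual.

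| Trigger | Wording | Named in 10.1? | Conflict with 10.2 |
|---|---|---|---|
| New anticancer therapy (4.6) | removed from the study | No | Direct |
| Pregnancy (8.3) | withdrawn from the study | No | Direct |
| No TMZ reduction left, starting level -2 or -3 (5.2.1) | off study, or pamiparib alone | Not at that point | Direct, if the first option is taken |
| Enzyme-inducing anti-epileptic (4.6.2) | removed from the protocol | No | Depends on the reading |

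On the third row, the nearest item in 10.1 is "Patients who require >2 dose reductions". The table reaches its off-study entry at the second reduction (level -2) or the first (level -3), and neither exceeds two. At starting levels 1 and -1 the table has no off-study entry, and a third reduction falls under 10.1 as off treatment. This trigger therefore arises only if Phase I de-escalates to -2 or -3.

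Both follow-up periods in 10.2 run from the off-treatment date. General items in 10.1, such as physician decision, could be used to set that date, but nothing directs sites to them for these triggers.

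**Illustration for PFS.** Every input here is an assumption: exponential PFS with median *m*, and a random fraction *f* of patients whose follow-up stops 0.5 month before progression. With λ = ln 2 / *m*, events at time *t* come only from the fraction 1 − *f*. The number at risk is proportional to (1 − *f*)S(*t*) + *f*·S(*t* + 0.5). The hazard that Kaplan-Meier estimates is therefore constant, and

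apparent median / true median = [(1 − *f*) + *f*·exp(−0.5λ)] / (1 − *f*).

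For *m* = 8 and *f* = 0.2: λ = 0.0866, exp(−0.0433) = 0.958, and the ratio is (0.8 + 0.2 × 0.958) / 0.8 = 1.24.

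| *f* | *m* = 4 | *m* = 8 | *m* = 12 |
|---|---|---|---|
| 0.10 | 1.10 | 1.11 | 1.11 |
| 0.20 | 1.23 | 1.24 | 1.24 |
| 0.30 | 1.39 | 1.41 | 1.42 |

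Simulation agrees with these ratios to within about 0.01. The ratio depends on *f* far more than on *m*, and the documents give no value for *f*.

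**Primary endpoint.** Exact binomial calculation reproduces the Section 11 designs. Arm A (0/15 stops, 4/25 rejects) gives early stopping 0.463 under the null and 0.013 under the alternative, type I error 0.034 and power 0.901. Arm B (≤7/24 stops, 22/53 rejects) gives 0.565, 0.032, 0.047 and 0.902. None of these uses the PFS or OS follow-up rules.

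**The case against.** The strongest reply is that 10.2 is the dedicated section and already controls. It permits survival status by phone call, clinic visit or medical records, and the treatment plans repeat the duty. No passage expressly tells a site to stop follow-up. The protocol also uses removal language loosely, since 10.1 itself, under off-treatment criteria, says: "Patients removed from study for unacceptable adverse events will be followed until resolution or stabilization of the adverse event". Section 8.3 likewise requires pregnancy follow-up after a patient has discontinued. Most of this stands. It makes loss of follow-up a risk rather than a planned step, and it protects OS better than PFS. It does not remove the conflict, because the looseness is what a site would have to interpret, and Section 11 has no rule to fall back on.

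Two stronger readings are tempting, and the documents support neither.

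- A reader might infer that all these triggers select patients who are doing badly. Only new anticancer therapy clearly fits. Exhausted reductions reflect toxicity, and pregnancy is not a marker of tumor prognosis. Use of an enzyme-inducing drug is only loosely linked, and 4.6.2 directs that only non-inducing drugs be started or added. Many patients needing salvage therapy will also have progressed already, with the PFS event recorded.
- A reader might infer a sizeable OS bias. A simulation with an assumed 24-month median, 10% to 30% of patients removed during months 1 to 12, and a 1.5- to 2.5-fold hazard afterwards overstates median OS by 0.8 months (24.0 against 23.2) to 4.6 months (24.0 against 19.4). It assumes that survival contact is lost for every removed patient, contrary to 10.2, so it is not an estimate for this plan.

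**Conclusion.** The inconsistency is real. Sections 4.6 and 8.3, and the 5.2.1 table at starting levels -2 and -3, conflict with 10.2; Section 4.6.2 is ambiguous. Information is lost only where a site follows the removal wording over 10.2 and 4.1 to 4.3.

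The practical exposure is mainly PFS, in patients who start new anticancer therapy before progression is called. The bias would be upward, provided that such patients are at higher risk of early progression than those who remain, which is plausible but not documented. OS is exposed only if survival contact also stops. The size is unknown: the 10% to 42% range shows sensitivity to assumed removal rates and is not a forecast.

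PFS and OS are secondary endpoints in Arms A and B and exploratory in the GBM arm. The primary response-rate decision rules are not shown to be affected. The correction is worth making because it is cheap and the missing PFS rule cannot be supplied neutrally once data are in.

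**What to change.** Reconcile the passages without changing when treatment stops:

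1. In 4.6, 4.6.2, 8.3 and the 5.2.1 table, replace the removal, withdrawal and off-study wording with *off protocol treatment*. Leave the clinical triggers and the options in the table as they are.
2. Name these triggers in 10.1, so that the 10.2 follow-up periods have a defined start date.
3. In 10.2, state that progression and survival follow-up continues after each of them. Amend the death-only sentence to allow withdrawal of consent to follow-up, since 10.0 already grants a right to withdraw.
4. In Section 11, state how PFS treats patients who start new anticancer therapy before documented progression. Continued follow-up alone does not settle this.

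The cost is minor wording and edits to the off-study reasons on the case report form, with no follow-up beyond what 10.2 already requires.

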4.6.1 Prohibited/Restricted Concomitant Medications during Study

There must be a period of at least 10 days from discontinuation of prohibited drugs and initiation of therapy unless otherwise specified in the protocol. Requests for specific exceptions to the required wait time can be submitted to the ABTC Central Office by providing a pharmacological rationale that the washout period for a particular drug should be less than 10 days (or as specified in the protocol); this must be approved by the ABTC Central Office.

The primary metabolic pathway for pamiparib (BGB-290) involves the CYP3A isoform. The compounds/substances below are prohibited, as they are associated with possible interactions with pamiparib (BGB-290) through the CYP3A metabolic pathway, as well as other various metabolic interactions. Based on preliminary *in vitro* screening assays,

NCI # ABTC-1801

PI: [name]

pamiparib (BGB-290) is a moderate inhibitor of CYP2C9 (IC₅₀ = 6.48 μ M). Investigators need to be aware that pamiparib (BGB-290) has the potential to interfere with the appropriate metabolism of medications that rely on CYP2C9 and follow the prescribing information recommendations for use with CYP2C9 inhibitors. Examples of these medications are also listed below, and these should be used cautiously with drug concentration monitoring where appropriate. In addition to CYP3A, pamiparib (BGB-290) can also be metabolized by CYP2C8 in human liver microsomes, but to a lesser extent. See below for medications that should be used with caution for the above reasons.

A handout with information for patients, their caregivers and non-study healthcare providers on possible interactions with other drugs and herbal supplements can be found in Appendix II, Patient Drug Information Handout and Wallet Card.

Prohibited Medications

The following medications and/or therapies should **not** be administered within the timeframes specified prior to enrollment and during the study:

Strong and moderate CYP3A inhibitors and Strong CYP3A inducers

Strong CYP3A Inhibitors:

Antibiotics: clarithromycin, telithromycin, troleandomycin Antifungals: itraconazole, ketoconazole, posaconazole, voriconazole Antivirals: boceprevir, telaprevir Other: cobicistat, conivaptan, elvitegravir, mibefradil, nefazodone Protease Inhibitors: indinavir, lopinavir, nelfinavir, ritonavir, saquinavir, tipranavir

Moderate CYP3A Inhibitors: Antibiotics: ciprofloxacin, erythromycin Antifungals: fluconazole Protease inhibitors: amprenavir, atazanavir, darunavir, fosamprenavir Calcium channel blockers: diltiazem, verapamil Tyrosine kinase inhibitors (anticancer): imatinib Food products: grapefruit juice (citrus 38aradise fruit juice) Herbal medications: Schisandra sphenanthera Others: aprepitant, casopitant, cimetidine, cyclosporine, dronedarone, tofisopam

Strong CYP3A Inducers:

Avasimibe, carbamazepine, mitotane, phenobarbital, phenytoin, firabutin, rifampin (rifampicin), St. John's wort (hypericumperforatum)

Medications to be used with caution

Sensitive CYP2C9 Substrates or CYP2C9 Substrates with Narrow Therapeutic Index: Celecoxib Phenytoin Warfarin

ABTC # 1801

NCI # ABTC-1801

PI: [name]

Strong CYP2C8 Inhibitors: Gemfibrozil

Herbal and Non-Traditional Medications

No data exist regarding the interaction of pamiparib (BGB-290) with commonly used herbal or non-traditional medications. Patients should be instructed not to use such medications while receiving pamiparib (BGB-290) therapy.

4.6.2 Anticonvulsants

No data exist regarding the interaction of pamiparib (BGB-290) with enzyme-inducing anti-epileptic drugs (EIAEDs). For this study, patients may **not** be on EIAEDs; patients who require anti-epileptic drugs (AED) may be on non-enzyme inducing anti-epileptic drugs (NEIAED). If a patient on this study protocol needs to have an AED started or needs to have a second AED added then only NEIAED should be used. There must be a ≥ 10 day period from discontinuation of an EIAED and initiation of therapy. In the event that an EIAED drug must be used for a patient on study the patient will be removed from the protocol.

4.6.3 Corticosteroids

Postoperatively, corticosteroids should be tapered to a stable dose as determined by the clinical status of the patient. The lowest required steroid dose should be maintained throughout the duration of the study in order to eliminate steroid effects as a confounding variable in the interpretation of serial brain imaging studies. Corticosteroid doses can be tapered as clinically indicated if the patient appears to be responding to therapy as judged by serial scans. Corticosteroid dose may, of course, be increased in the event of clinical deterioration or at the discretion of the attending physician. In the event of suspected clinical deterioration, repeat brain imaging is recommended.

4.6.4 Antiemetics

The use of any antiemetic deemed necessary for the care of the patient is allowed. The prophylactic use of a 5-HT3-antagonist or metoclopramide is strongly recommended before temozolomide administration.

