6.0 PHARMACEUTICAL INFORMATION

6.1 Pamiparib (BGB-290) (NSC# 803412)

Chemical Name: (R)-2-fluoro-10a-methyl-5,8,9,10,10a,11-hexahydro-5,6,7a,11-tetraazyacyclohepta[def]cyclopenta[a]fluoren-4(7H)-one

Molecular Formula: C₁₆H₁₅FN₄O

Molecular Mass: 298

Mode of Action: highly potent and selective PARP inhibitor, binds to PARP enzyme and prevents PARP-mediated repair of single-stranded DNA breaks via base-excision repair, thus enhancing the accumulation of DNA double strand breaks.

NCI # ABTC-1801

PI: [name]

How Supplied: supplied by BeiGene Ltd. pamiparib (BGB-290) pellet-in-capsules are provided in a container with a child-resistant closure. Each container is labeled with space to enter the subject's ID, treatment and period number. The label is pre-printed and includes content and quantity of pamiparib (BGB-290), protocol number, batch number, administration instructions, storage instructions and expiry date. Subjects will receive pamiparib (BGB-290) as 10 mg, 20 mg or 40 mg capsules, depending on dose level and availability.

Storage: Pamiparib (BGB-290) must be kept at 15°C to 30°C. An accurate study drug accountability log must be maintained and kept up to date at all times.

Stability: Pamiparib (BGB-290) is an oral formulation. The drug should be stable at minimum until the expiration date on the bottle.

Route of Administration: Pamiparib (BGB-290) is taken by mouth with 8 ounces of water while fasting.

Known Potential Drug Interactions: Strong and moderate CYP3A inhibitors and strong CYP3A inducers are prohibited due to potential for drug interactions. Strong CYP2C8 inhibitors and sensitive CYP2C9 substrates or CYP2C9 substrates with narrow therapeutic index should be used with caution.

Contraindications: Pamiparib (BGB-290) should not be used in patients who are pregnant.

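### Section 4.6.4 permits every antiemetic, although Section 4.6.1 bans aprepitant and casopitant by name and no rule says which section governs

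*Combined protocol and SAP*

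**What the plan says.** **The permission.** Section 4.6.4 states: "The use of any antiemetic deemed necessary for the care of the patient is allowed". It goes on to recommend prophylaxis with a 5-HT3 antagonist or metoclopramide before temozolomide. It names no excluded antiemetic and does not refer to Section 4.6.1.

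**The ban.** Section 4.6.1 says that the listed drugs should not be "administered within the timeframes specified prior to enrollment and during the study". The banned classes are strong and moderate CYP3A inhibitors and strong CYP3A inducers. The moderate-inhibitor list ends with "Others: aprepitant, casopitant, cimetidine, cyclosporine, dronedarone, tofisopam". The reason is given in the same section: "The primary metabolic pathway for pamiparib (BGB-290) involves the CYP3A isoform". Section 6.1 repeats the rule by class, without naming drugs: "Strong and moderate CYP3A inhibitors and strong CYP3A inducers are prohibited due to potential for drug interactions".

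**Phenytoin.** Section 4.6.1 puts it among the banned strong inducers ("Avasimibe, carbamazepine, mitotane, phenobarbital, phenytoin, firabutin, rifampin"). It appears again among the CYP2C9 substrates to be used with caution ("Celecoxib Phenytoin Warfarin"), of which the section says "these should be used cautiously with drug concentration monitoring where appropriate".

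**The concern.** For two drugs, aprepitant and casopitant, one section of the protocol gives permission and another forbids. The section that gives permission is the one headed Antiemetics, so a clinician treating nausea is likely to look there first. Antiemetic use is expected in this trial, since prophylaxis is recommended in both 4.5.2 and 4.6.4.

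What is at stake is patient safety and clean exposure to the investigational drug. The ban protects pamiparib's main route of metabolism. A literal reading of 4.6.4 would let a site give an inhibitor of that route while believing that it was following the protocol.

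**Working it through.** No arithmetic applies. The check is whether the sections can be read together, and whether any text settles the conflict.

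1. **Do the two rules cover the same drugs?** Section 4.6.4 covers every antiemetic. Section 4.6.1 bans aprepitant and casopitant by name. The documents do not themselves call these two drugs antiemetics; I take that as undisputed drug-class knowledge. On that basis both drugs fall under both rules.

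2. **Do the rules cover the same period?** The 4.6.1 ban runs before enrollment and throughout the study. The 4.6.4 permission applies to care on study. They overlap for the whole of treatment.

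3. **Does the general rule in 4.6 settle it?** No. It lets the investigator give medically necessary drugs, and the exceptions it states are anticancer treatments (chemotherapy, radiotherapy, biological therapy) and other investigational agents. CYP3A inhibitors are not among them.

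4. **Does the exception process in 4.6.1 settle it?** No. It lets a site ask the ABTC Central Office for a washout shorter than 10 days. It concerns the waiting time before treatment starts, not use during treatment.

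5. **Does Section 6.1 settle it?** It confirms that the class ban is meant. It does not mention antiemetics and does not say that it overrides 4.6.4.

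6. **Is compliant prophylaxis available?** Yes. Neither the 5-HT3 antagonists (4.5.2 and 4.6.4) nor metoclopramide (4.6.4) appears on the prohibited lists in 4.6.1.

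7. **Can the effect be sized?** No. The documents give neither the change in pamiparib exposure under a moderate CYP3A inhibitor nor an expected frequency of use. Any figure would be invented.

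8. **Is phenytoin a conflict of the same kind?** It is listed twice, and the caution entry implies that it may be used. Other text settles the matter, however. Section 3.3 item 7 makes patients on enzyme-inducing anti-epileptics ineligible. The 4.6.1 inducer list bans phenytoin by name. Section 4.6.2 allows only non-inducing drugs to be started or added, and removes a patient who must take an inducer.

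**The case against.** The strongest reply is that 4.6.4 is a general permission to be read under a specific ban. Section 4.6 is drafted in the same way: it gives a broad permission, and 4.6.1, whose title announces prohibited and restricted drugs, then narrows it. On that reading the intended rule is not in doubt, and 4.6.4 merely lacks a cross-reference. I accept that the ban is what was intended. The reply does not remove the point, because the protocol states no order of precedence, and 4.6.4 is itself the specific section on antiemetics and uses an unrestricted term.

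A second reply is that the situation would be uncommon. A site would have to go beyond the recommended agents and also overlook 4.6.1. Section 4.6.1 also refers to a patient handout and wallet card on interactions in Appendix II; that appendix is not in the text I worked from, so I cannot say whether it names these drugs. Section 5.1 excludes from the DLT definition events assessed as related to concomitant medication, which gives dose finding some protection if the interaction is recognised. All of this stands and limits the practical risk.

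Three stronger readings are tempting, and the documents do not support them:

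- A reader might count phenytoin as a third drug with equally conflicting instructions. The caution list addresses a different question, namely what pamiparib may do to CYP2C9 substrates. A site would have to ignore several explicit bans to be misled.
- A reader might add that no pamiparib levels are sampled during combination cycles, so an interaction would go unseen. The sampling in 9.1.2 and 9.5.2 serves the surgical tissue-concentration objective and was not designed to detect interactions. The absence of other samples is no evidence of this defect, and correcting 4.6.4 would not change it.
- A reader might infer that toxicity or response results will be distorted. With neither interaction size nor frequency of use in the documents, that cannot be shown.

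**Conclusion.** The point holds as an inconsistency in the concomitant-medication rules. Followed literally, 4.6.4 permits two drugs that 4.6.1 bans because of pamiparib's CYP3A metabolism, and nothing in the protocol says which section prevails. It is worth correcting because it bears on patient safety and the correction costs almost nothing.

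Its size is modest. It concerns aprepitant and casopitant only, and no numerical consequence can be derived. It leaves the design, endpoints, sample size, error rates and analysis unchanged. The conclusion rests on two assumptions: that both drugs are antiemetics, and that no text outside what could be read, such as Appendix II, sets the order of precedence. The double listing of phenytoin is an editorial slip and adds no weight.

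**What to change.** In Section 4.6.4, add to the permission: *except drugs prohibited in Section 4.6.1 (e.g., aprepitant, casopitant)*. As a minor tidy-up, delete phenytoin from the caution list in Section 4.6.1.

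The cost is one phrase and one word at the next amendment. Clinically, a patient who would have received aprepitant or casopitant needs another antiemetic; the agents already recommended remain available.
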